10.2.6.4 Safety Dataset

The Safety dataset will include all participants who are randomized in to the study and administer at least one dose of study gel. This dataset will be employed to determine all safety endpoints. Participants will be analyzed according to the actual study treatment received.

10.2.6.5 Per-Protocol (PP) Dataset

The Per-Protocol dataset is a subset of the Modified Intent-to-Treat dataset which includes all randomized participants who administered at least 6 doses of study product over 7 consecutive

days and who are considered sufficiently compliant with the protocol. All primary and secondary efficacy evaluations will be conducted in the Per-Protocol Dataset as supportive to the MITT analysis.

The definition of "sufficiently compliant" includes, but is not limited to:

- No violations of any study entry eligibility criteria;
- Received study treatment to which they were randomized and did not receive the wrong medication or incorrect dose at any time;
- ≥85% compliant to intended dose of Investigational Product;
- Did not receive any excluded concomitant medication prior to the time point evaluated;
- Treatment assignment was not unblinded to the subject, study site personnel, CRO, or Sponsor at any time during the study.

The criteria may be amended prior to unblinding of treatment assignment and analysis of data. Reasons for changes may include study conduct changes, protocol amendments, or changes in the appropriateness of the criteria, which may be assessed based on review of blinded data.

10.2.6.6 Microbiological Dataset

The microbiological dataset is a subset of the Intent-to-Treat dataset which includes participants that have at least one sample collected for semi-quantitative analysis of vaginal microflora.

10.3 Exclusion of a Study Participant from Statistical Analysis

Analysis and reporting of the study is to be conducted strictly in accordance with the Statistical Analysis Plan, and is to include all study participants fulfilling the definition of the datasets indicated above. Any decisions regarding the "evaluability of participants" is to be made in a blinded review of the data before database lock and agreement to exclude a particular participant's data from a dataset is to be clearly documented with a reason in the Study File and Final Study Report.

10.4 Sample Size Justification

Primary analysis will be a comparison of 0.5%, 1% and 3% SPL7013 Gel vs. HEC placebo gel with each treatment regimen. Assuming Clinical Cure rates of 50% and 15% for SPL7013 Gel and HEC placebo gel, respectively, a sample size of a minimum of 28 evaluable subjects per treatment arm will provide 80% power to detect a treatment difference with a final alpha significance level of 0.048. It is estimated that there will be a 15% drop-out rate which provides 33 patients to be randomized per treatment arm and 132 patients overall in the study.

The primary hypothesis will be:

Null Hyothesis (Ho): Clinical cure rate at TOC will be the same for both SPL7013

Gel and Placebo treated groups

Alternate Hypothesis (Ha): Clinical cure rate at TOC will be different between SPL7013

Gel and Placebo treated groups

An interim analysis has been included in the sample size design using the using the O'Brien-Fleming method with the significance level calculated for the final analysis being 0.048.

10.5 Planned Interim Analysis

When 50% of patients have completed TOC at Day 9-12 visit, an interim analysis will be conducted to provide guidance in the decision of which dose groups to include in a forthcoming protocol based on preliminary efficacy results. The interim analysis will be carried out using the O'Brien-Fleming method with α =0.005 for the interim analysis and α =0.048 for the final analysis.

The interim analysis will be analyzed by an independent statistician not otherwise involved in the study. Full details of data to be analyzed and procedures for unblinding including dissemination of results will be presented in the statistical analysis plan.

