| Study Procedures: | After a maximum 1 week screening period, participants will be randomized to receive either 0.5%, 1% or 3% SPL7013 Gel or HEC placebo gel at a dose of 5g each night administered vaginally for 7 consecutive days. Participants will be assessed for BV (both clinically by Amsel's criteria and microbiologically by Nugent score) at screening, baseline (screening and baseline may be combined), after last | | |

application (Day 9-12) and at the final study visit (Test of Cure, TOC visit) approximately 2-3 weeks after last dose (Day 21-30).

At each visit participants will undergo: pelvic/gynecological examination, during which cervical and vaginal swabs will be taken (including a swab for a storage sample); adverse events will be recorded; and adherence to the protocol will be assessed. Acceptability Questionnaires will be administered at the end of the treatment period (Visit 3, Day 9-12), and Symptom Questionnaires at each visit. Participants will complete Diary Cards on a daily basis to capture data on study drug administration and compliance, and adverse events.

Women who report no improvement in their BV-associated discharge by Visit 3 (Day 9-12), and wish to receive further treatment will be offered rescue therapy in line with local practice, after all visit assessments have been completed. Rescue therapy may also be offered to women who relapse.

Safety Parameters:

Urinalysis, physical and pelvic/gynecological examination, medical history, AEs (as graded by the DAIDS toxicity tables), semi-quantitative analysis of vaginal flora (sub-set only).

Statistical Analyses:

Primary analysis will be a comparison of 0.5%, 1% or 3% SPL7013 Gel vs. placebo gel. Assuming Clinical Cure rates of 50% and 15% for SPL7013 Gel and placebo gel, respectively, a sample size of a minimum of 28 evaluable subjects per treatment arm will provide 80% power to detect a treatment difference with an alpha significance level of 0.05.

When 50% of patients have completed TOC at Day 21-30 visit, an interim analysis will be conducted to provide guidance in the decision of which dose groups based on preliminary efficacy and safety to include in a forthcoming protocol. The interim analysis will be carried out using the O'Brien-Fleming method with α =0.005 for the interim analysis and the significance level calculated for the final analysis being 0.048.

Table 1 Schedule of Study Assessments

| | May be combined | | | |

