7.1.3 Visit 3 (Day 9-12)

Visit 3 will be scheduled for Day 9-12, after completion of treatment. This visit should be scheduled prior to the anticipated date of onset of menses. If menses is due to occur or actually occurs on Day 9 then the visit may be delayed until complete cessation of bleeding.

This visit will include the following procedures:

- Review of protocol compliance
- · Review diary card
- Review of AEs and concomitant medications (see Sections 7.3.5 and 8)
- Completion of Symptom Questionnaire (see Section 7.2.7)
- Completion of Acceptability Questionnaire [TSQM] (see Section 7.2.8)
- Pelvic examination including vaginal swab for Gram stain, semi-quantitative analysis (subset only) and storage sample (see Sections 7.2.3 and 7.2.6)
- Assessment of BV according to the Amsel's Criteria
- Issue diary card for follow-up period and provide instructions for completion
- Collect used and unused applicators

Women who report no improvement in vaginal discharge associated with BV who wish to receive further treatment will be offered rescue therapy according to Section 6.8. These study participants will be considered "Treatment Non-Responders", and will not attend the TOC visit. Instead, these participants will receive a telephone call at the time that the TOC would be scheduled to assess response to rescue medication and any adverse effects (*e.g.* candidiasis). Participants will be referred to their primary care physician for any ongoing AEs as appropriate. Any ongoing SAEs should be followed until resolution.

Each participant is then provided with the date of the last scheduled visit, the Follow-Up visit.

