7.1.4 Visit 4 (Day 21-30) – Test of Cure (TOC)

Visit 4 (TOC) will be scheduled for Day 21-30, and will include the following procedures:

- Review of protocol compliance
- Review diary card
- Review of AEs and concomitant medications (see Sections 7.3.5 and 8). Participant will be referred to her primary care physician for any ongoing AEs as appropriate. Any ongoing SAEs should be followed until resolution or considered as stable.
- Completion of Symptom Questionnaire
- Pelvic examination including vaginal swab for Gram stain, semi-quantitative analysis (subset only), and storage sample (see Sections 7.2.3 and 7.2.6)
- Assessment of BV according to the Amsel's Criteria. Women who suffer a recurrence of BV symptoms who wish to receive further treatment will be provided with treatment for her BV according to local practice (see Section 6.8). Any rescue therapy will be documented in the participant's CRF.
- Pregnancy testing (see Section 7.2.6)

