10.6 Randomization and Blinding Procedures

Participants will receive either 0.5%, 1% or 3% SPL7013 gel or HEC placebo gel depending upon the randomization schedule.

Randomization of the allocation of each study product will be performed by an independent statistician employing a randomly permuted block design. Participants will be assigned a PIN upon randomization, and this number will link to the study product allocated.

The study is double-blind, *i.e.*, study staff and participants will be blinded to the random assignment of product to all study participants. All study products be supplied in identical packaging. Blinding will be maintained until all data are entered in to the study database, all study endpoint data and other data included in the final analysis have been cleaned and verified, and the data are ready for final analysis. This will be explained to participants as part of the study. The only person(s) to whom the study will be unblinded during its duration will be the independent statistician(s) preparing the randomization list.

There are no circumstances under which it is expected that unblinding will be necessary for the provision of medical treatment or to otherwise protect the safety of study participants. As described in Section 9.4 in the event that an Investigator is concerned that a participant might be put at undue risk by continuing product use, the Investigator may discontinue use for the participant concerned.

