10.8 Statistical and Analysis Plan

A final statistical analysis plan will be developed and approved by Starpharma prior to database lock. Statistical analyses will be performed after all participants have ended their participation in the study. Participants withdrawn prior to randomization will not be assessed for outcome variables or safety parameters. The following is a summary of the planned analyses; full details are captured in the statistical analysis plan. Any deviations to be made from this summary plan and planned analyses will be documented in the statistical analysis plan.

All hypotheses will be tested for statistical significance with two-tailed p-values unless otherwise noted. Results of all tests will be considered statistically significant if their p-value is less than or equal to 0.048 as per the O'Brien-Fleming α adjustment for the planned interim analysis.

Continuous variables will be summarized using descriptive statistics (N, mean, standard deviation, median, minimum and maximum), while categorical variables will be summarized as counts and percentages of participants in each category. Results will be presented by treatment group as appropriate.

Efficacy analyses will be presented using the MITT and per-protocol populations. For efficacy analyses, all missing values due to participant withdrawal and missed visits as well as values outside of analysis windows will be imputed using the last observation carried forward (LOCF) method as appropriate. For sensitivity analysis, efficacy results will also be presented with "as observed" results.

All baseline and demographic summaries will be based on the MITT dataset. No statistical comparisons between treatment groups will be made on demographic and baseline characteristics.

If there is a discrepancy between the locally and centrally read Nugent score, the locally read score will take precedence over the centrally read score in determining whether a participant is eligible to enter the study. The centrally read score will take precedence over the local score in determining study endpoints.

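### Section 10.5 starts the interim analysis at a test-of-cure visit on Day 9-12 that does not exist, and the SAP deadline and blinding text do not accommodate the interim

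*Protocol*

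**What the plan says.** **Trigger.** Section 10.5: "When 50% of patients have completed TOC at Day 9-12 visit, an interim analysis will be conducted". Synopsis, Statistical Analyses: "When 50% of patients have completed TOC at Day 21-30 visit, an interim analysis will be conducted". Section 7.1.4: "Visit 4 (TOC) will be scheduled for Day 21-30". Section 7.1.3: "Visit 3 will be scheduled for Day 9-12, after completion of treatment". Table 1 and Section 4 agree with Section 7.1.4 on when TOC takes place.

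**Levels and purpose.** Section 10.5 sets "α =0.005 for the interim analysis and α =0.048 for the final analysis" by the O'Brien-Fleming method. The look is meant to guide which dose groups go into a later protocol. The primary endpoint is Clinical Cure at TOC (Sections 3.1 and 10.2.1). Clinical Cure at Visit 3 is secondary (Sections 3.2 and 10.2.2).

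**Who is unblinded.** Section 10.5 gives the interim to an independent statistician with no other role in the study. Section 10.6 states: "The only person(s) to whom the study will be unblinded during its duration will be the independent statistician(s) preparing the randomization list".

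**When the rules are fixed.** Section 10.5 leaves the interim's data, unblinding procedures and dissemination of results to the SAP. Section 10.8 states: "A final statistical analysis plan will be developed and approved by Starpharma prior to database lock". It also lets the SAP record departures from the protocol's planned analyses. On the Per-Protocol criteria, Section 10.2.6.5 states: "The criteria may be amended prior to unblinding of treatment assignment and analysis of data".

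**The concern.** The sentence that starts the interim joins the name of one visit to the day range of another, so it does not settle which visit must be complete or which visit's outcome is tested. If the day range is followed, there are two possibilities. The test may use Clinical Cure at Visit 3, in which case the 0.005 boundary is not a look at the primary endpoint. Or it may use Clinical Cure at TOC with fewer than half the women contributing. In the first case the choice of doses would rest on response just after treatment, when the trial defines success as cure two to three weeks after the last dose. Section 2.1 itself says that relapse after BV therapy is common.

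The other two gaps concern control of the look. The protocol's list of unblinded persons leaves out the one who must be unblinded to run the interim. And the document that is to hold the interim rules has no deadline tied to the interim.

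**Working it through.** **1. Which visit is TOC?**

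| Place in Protocol | Day 9-12 | Day 21-30 |
|---|---|---|
| Table 1 | Visit 3, end of treatment | Visit 4, TOC |
| Section 4 | assessment after last application | TOC |
| Sections 7.1.3 and 7.1.4 | Visit 3 | Visit 4, TOC |
| Synopsis, interim sentence | – | TOC |
| Section 10.5, interim sentence | TOC | – |

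Section 10.5 is alone in linking TOC to Day 9-12.

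**2. Reproduce the plan's own figures.** Inputs from Section 10.4: cure rates 50% and 15%, final two-sided level 0.048, 80% power, 15% drop-out.

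- A two-proportion test with pooled variance and no continuity correction needs 28 per arm; power at 28 is 81.1%.
- 28 / 0.85 = 32.9, so 33 per arm; 4 × 33 = 132.
- A classical two-look O'Brien-Fleming design uses boundaries c·√2 and c, with c chosen so that the total two-sided error is 0.05 at information fraction t = 0.5. This gives c = 1.977, hence levels 0.0052 and 0.0480, which round to the stated 0.005 and 0.048.
- The total error with the stated levels is 1 − P(|Z1| < 2.807 and |Z2| < 1.977), where corr(Z1, Z2) = √t. At t = 0.5 it is 0.0499.

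The stated levels therefore belong to a look at half the primary-endpoint information: 0.5 × 132 = 66 women with a TOC result. That is the Synopsis trigger.

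**3. What a Day 9-12 trigger would do to t.** TOC follows Visit 3 by 21 − 12 = 9 to 30 − 9 = 21 days. The midpoints of the windows differ by 25.5 − 10.5 = 15 days. The protocol gives no accrual rate, so uniform accrual of 132 women is assumed here, with

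t = (66 − 132 × 15 / D) / 132, where D is the accrual time in days.

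| Assumed accrual | Women still awaiting TOC | t | Total two-sided error |
|---|---|---|---|
| 3 months (91 days) | 21.8 | 0.335 | 0.0509 |
| 6 months (182 days) | 10.9 | 0.418 | 0.0504 |
| 12 months (365 days) | 5.4 | 0.459 | 0.0502 |

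At t = 0.3 the total is 0.0511. If information is counted against the 112 women expected to be evaluable (Section 5.1.4), 66 with TOC gives t = 66 / 112 = 0.59 and a total of 0.0494. On any of these counts the error stays close to 0.05.

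**4. Blinding and timing, side by side.** Section 10.6 limits unblinding during the study to those who prepare the randomization list. Section 10.5 assigns a by-dose analysis to someone with no other part in the study. Both cannot be true as written. Section 10.5 needs SAP content at the interim, while Section 10.8 asks for the SAP only by database lock. Section 10.2.6.5 closes changes to the Per-Protocol criteria at unblinding but does not say whether the interim counts as that unblinding.

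**The case against.** The best defence is that Section 10.5 contains a slip. It names TOC, every other place puts TOC at Day 21-30, the Synopsis sentence is nearly identical with the right window, and the alpha levels fit that reading. This is probably what was intended. But Section 10.5 is the operative section, and it should not need inference to be carried out.

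Four stronger readings are tempting and should not be drawn:

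- **Pending TOC results would be filled with Day 9-12 values.** Section 10.8 limits last-observation-carried-forward to withdrawals, missed visits and values outside the analysis windows. A visit not yet due is none of these, and as-observed results are planned as well.
- **Analysis sets can be reshaped after the interim results are known.** The amendment clause covers only the Per-Protocol set, which supports the modified intent-to-treat analysis, and changes must precede unblinding. Section 10.3 requires evaluability decisions in a blinded review. What stands is that the interim's status under that clause is not stated.
- **The sponsor will be unblinded while settling the rules.** Dissemination is left to the SAP, which is not at hand. The purpose of the look suggests that by-dose results reach decision makers, but the protocol does not say who they are.
- **The type I error is seriously inflated.** The calculation shows otherwise, and Section 10.5 gives no rule for stopping this trial.

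It is also fair to say that interim content placed in the SAP implies that this part exists before the look, with database lock as an outer limit for the final version. No sentence makes that binding.

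**Conclusion.** The trigger in Section 10.5 is wrong as written and contradicts the Synopsis, Table 1 and Sections 4 and 7.1.4. Only the Day 21-30 reading fits the stated levels, counting 66 of 132 women. Under a Day 9-12 reading that tests TOC, the information fraction falls to roughly 0.34 to 0.46 and the total error becomes about 0.0502 to 0.0509. Those figures rest on assumed uniform accrual over 3 to 12 months and a 15-day lag. The consequence that counts is not numerical: the look that guides dose choice could rest on a secondary, early endpoint.

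The conflict between Sections 10.5 and 10.6 is real but is one of wording. The SAP deadline leaves the interim rules without a date. It permits late finalisation, but nothing shows that late finalisation is planned. The sample size is not affected. This should be fixed before the interim takes place; it does not undermine the design.

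**What to change.** - **Section 10.5:** trigger the interim when 50% of patients (66) have completed the TOC visit (Visit 4, Day 21-30), and base the interim efficacy test on those women's TOC outcomes.
- **Sections 10.8 and 10.2.6.5:** require the SAP, including the interim rules and the Per-Protocol criteria, to be signed before the interim data cut.
- **Section 10.6:** add the interim statistician to the unblinding exception, and state that anyone who receives interim results by dose takes no part in the blinded data review.

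Cost: changes of wording. Compared with a Day 9-12 trigger, the interim comes about two weeks later, and the SAP has to be ready earlier. Sample size and alpha levels stay as they are.

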10.6 Randomization and Blinding Procedures

Participants will receive either 0.5%, 1% or 3% SPL7013 gel or HEC placebo gel depending upon the randomization schedule.

Randomization of the allocation of each study product will be performed by an independent statistician employing a randomly permuted block design. Participants will be assigned a PIN upon randomization, and this number will link to the study product allocated.

The study is double-blind, *i.e.*, study staff and participants will be blinded to the random assignment of product to all study participants. All study products be supplied in identical packaging. Blinding will be maintained until all data are entered in to the study database, all study endpoint data and other data included in the final analysis have been cleaned and verified, and the data are ready for final analysis. This will be explained to participants as part of the study. The only person(s) to whom the study will be unblinded during its duration will be the independent statistician(s) preparing the randomization list.

There are no circumstances under which it is expected that unblinding will be necessary for the provision of medical treatment or to otherwise protect the safety of study participants. As described in Section 9.4 in the event that an Investigator is concerned that a participant might be put at undue risk by continuing product use, the Investigator may discontinue use for the participant concerned.

10.7 Safety Review

Safety review will occur throughout the study as outlined in Section 8.10.

10.8 Statistical and Analysis Plan

A final statistical analysis plan will be developed and approved by Starpharma prior to database lock. Statistical analyses will be performed after all participants have ended their participation in the study. Participants withdrawn prior to randomization will not be assessed for outcome variables or safety parameters. The following is a summary of the planned analyses; full details are captured in the statistical analysis plan. Any deviations to be made from this summary plan and planned analyses will be documented in the statistical analysis plan.

All hypotheses will be tested for statistical significance with two-tailed p-values unless otherwise noted. Results of all tests will be considered statistically significant if their p-value is less than or equal to 0.048 as per the O'Brien-Fleming α adjustment for the planned interim analysis.

Continuous variables will be summarized using descriptive statistics (N, mean, standard deviation, median, minimum and maximum), while categorical variables will be summarized as counts and percentages of participants in each category. Results will be presented by treatment group as appropriate.

Efficacy analyses will be presented using the MITT and per-protocol populations. For efficacy analyses, all missing values due to participant withdrawal and missed visits as well as values outside of analysis windows will be imputed using the last observation carried forward (LOCF) method as appropriate. For sensitivity analysis, efficacy results will also be presented with "as observed" results.

All baseline and demographic summaries will be based on the MITT dataset. No statistical comparisons between treatment groups will be made on demographic and baseline characteristics.

If there is a discrepancy between the locally and centrally read Nugent score, the locally read score will take precedence over the centrally read score in determining whether a participant is eligible to enter the study. The centrally read score will take precedence over the local score in determining study endpoints.

